3.3. Duration of Study

Qualifying subjects will receive BLI400 at Visit 1 and will begin a 12-month Treatment Period. Subjects will return for clinic visits at the end of Months 2, 4, 6, 9 and 12. A follow up call will take place 2 weeks after the end of treatment. A completed subject is defined as a subject that completes the Visit 6 (Month 12) visit.

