4.2.7. Follow-up Telephone Call (*Day 374*) +/- 4 days

At Day 374, approximately 2 weeks after the last study visit or early term visit, site personnel will contact subjects by telephone to query if any new adverse events have occurred and if any adverse events ongoing at Visit 6 have resolved. Subjects will also be asked about the status of their concomitant medications.

Braintree Laboratories, Inc.
Protocol Number BLI400-303

Confidential

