4.5. Concomitant Medications

The use of concomitant medication will be recorded from 7 days prior to Visit 1 until the end of the study at the telephone contact on Day 374. Subjects enrolled in this study will not be permitted to take any laxatives (other than the sponsor supplied rescue bisacodyl), whether prescription or over-the-counter, from Visit 1 until after completion of Visit 6. Any restricted laxative use during the study may result in termination of subject's participation. Subjects may not initiate treatment with any constipating medication.

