5. ADVERSE EVENTS

5.1. Adverse Event Definition and Reporting

An Adverse Event (AE) is any untoward medical occurrence associated with the use of a drug in humans, whether or not considered drug related. An AE can therefore be any unfavorable and unintended sign (including a clinically significant abnormal laboratory finding), symptom, or disease temporally associated with the use of a medicinal (investigational) product.

Adverse event collection will coincide with the subject providing informed consent to participate in the study and will conclude with the end of study participation at Day 374 Follow-up Call. Diarrhea should be reported as an adverse event if a subject has more than 3 watery stools per day. Subjects with clinically significant laboratory results at Visit 6 which are classified by the Investigator as adverse events should return for a repeat blood draw. Subjects will be instructed to report promptly adverse events to the Investigator. The Investigator will record date/time of report, date/time of onset, description of the adverse event, severity of adverse event, action(s) taken regarding treatment of the event, action(s) taken regarding study participation, duration of adverse event, and the Investigator's assessment of relationship of adverse event to study treatment.

The Investigator should assess the severity of each adverse event using the following categories:

Grade	Severity	Description
1	Mild	Barely noticeable, does not influence functioning Causing no limitations of usual activities
2	Moderate	Makes participant uncomfortable, influences functioning Causing some limitations of usual activities
3	Severe	Severe discomfort, treatment needed Severe and undesirable, causing inability to carry out usual activities
4	Life threatening	Immediate risk of death Life threatening or disabling
5	Fatal	Causes death of the participant

Braintree Laboratories, Inc.
Protocol Number BLI400-303

Confidential

The Investigator should assess the relationship to study drug for each adverse event using the following categories:

Categories of Attribution:	Description
UNRELATED	There is no evidence of any causal relationship.
POSSIBLE	There is some evidence to suggest a causal relationship (e.g., the event occurred within a reasonable time after administration of the trial medication). However, the influence of other factors may have contributed to the event (e.g., the patient's clinical condition, other concomitant events).

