6. SERIOUS ADVERSE EVENTS REPORTING

A Serious Adverse Event (SAE) is any untoward medical occurrence that results in at least one of the following outcomes:

- Results in death
- Is life-threatening
- Requires inpatient hospitalization or prolongation of existing hospitalization
- A persistent or significant incapacity or substantial disruption of the ability to conduct normal life functions
- Is a congenital anomaly/birth defect
- Requires medical or surgical intervention to prevent permanent impairment or damage

SAE collection will coincide with the subject providing informed consent to participate in the study and will conclude 30 days after a subject's last dose of study medication. Should a serious and/or unexpected adverse event occur, the Investigator must notify Braintree Laboratories immediately. The Investigator will make a decision regarding continuing the subject's study participation, and may request input from Braintree Laboratories. The Investigator will be responsible for recommending or providing the subject with appropriate medical therapy. All subjects experiencing serious adverse events will be followed until satisfactory resolution occurs. Braintree Laboratories must be kept apprised of all follow-ups relative to serious adverse events. In addition, Investigators must comply with the SAE reporting requirements of the Institutional Review Board with oversight of the study.

Any serious and/or unexpected adverse events that occur during the study will be reported to Braintree Laboratories as follows:

Contact Telephone Numbers:

During Business hours (M-F, 8:30 am – 5:00 pm EDT)	[contact]
After hours or weekends	[contact]

Braintree Laboratories and its medical monitor will review the report and determine whether an FDA Form 3500A will also be completed and sent to FDA.

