9.3.2. Safety Analyses

Analysis of safety will be performed using the modified Intent to Treat population (see [Section 9.4](#)).

Adverse Events

Adverse Events will be coded using the MedDRA classification to provide a preferred term and primary system organ class for each event. Proportions of subjects with adverse events will be presented for the overall study population, and each demographic subgroup (age, gender and race). Tables of AEs will be presented by system organ class and preferred term, and include overall totals for AEs within each system organ class. Counting will be done by subject and not by event. A table of counts and percentages will also be made of those subjects with SAEs or AEs which led to withdrawal from the study.

Treatment-emergent AEs are defined as adverse events that had an onset day and time on or after the day and time of the first dose of study drug until the Day 374 Follow-up Call. Adverse Events having missing onset dates will be considered as treatment emergent.

The difference in adverse event rates between study periods will be tested by Chi-Square or Fisher's exact test with 95% confidence intervals.

Laboratory Parameters

Summary statistics (i.e., mean, minimum, maximum, standard deviation, and number of subjects) will be presented for each laboratory parameter at each visit. Laboratory data will be summarized for the overall population and the elderly and non-elderly subgroups. When calculating the summary statistics only, the last observation within a visit window will be used if there are multiple observations. Changes from baseline (Visit 1) will be presented in a similar format. An additional listing will be provided of those subjects who have clinically significant laboratory values. The data will also be presented as shift tables and clinically significant abnormalities will be examined.

Results of laboratory tests for the change from baseline (Visit 1) and group differences will be tested using ANOVA.

Vital Signs

Summary statistics (i.e., mean, minimum, maximum, standard deviation, and number of subjects) will be presented for each vital sign at each visit and compared to the values obtained at Visit 1. When calculating the summary statistics only, the last observation within a visit window will be used if there are multiple observations. The data will also be presented as shift tables and clinically significant abnormalities will be examined.

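### Does ending the treatment-emergent window at the Day 374 call, when SAEs are collected to 30 days after last dose, need a change to the plan?

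*Combined protocol and SAP*

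**What the plan says.** Four parts of the protocol bear on this, and both copies in the combined document read the same.

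- **All adverse events.** Under Section 5.1, collection starts at consent and "will conclude with the end of study participation at Day 374 Follow-up Call". Section 4.5 records concomitant medication "until the end of the study at the telephone contact on Day 374", and the table in Section 4.3 shows no contact after that call.
- **SAEs.** Under Section 6, collection also starts at consent but "will conclude 30 days after a subject's last dose of study medication".
- **Timing of the call.** Section 3.3 says: "A follow up call will take place 2 weeks after the end of treatment". Section 4.2.7 says: "At Day 374, approximately 2 weeks after the last study visit or early term visit".
- **Analysis.** Section 9.3.2 defines treatment-emergent events as those with onset "on or after the day and time of the first dose of study drug until the Day 374 Follow-up Call". It then adds: "A table of counts and percentages will also be made of those subjects with SAEs or AEs which led to withdrawal from the study". Section 9.2 promises treatment-emergent rates by preferred term, severity and relationship.

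Section 5.1 also provides for self-reporting: "Subjects will be instructed to report promptly adverse events to the Investigator". Section 6 requires the investigator to notify the sponsor at once of a serious event and to follow it until it resolves satisfactorily.

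**The concern.** The collection rule and the analysis rule end on different days. Section 6 obliges the sponsor to collect SAEs for 30 days after dosing, yet nobody is scheduled to ask about them in roughly the second half of that time. An SAE that does surface then has no stated place in the analysis. It is not treatment-emergent under Section 9.3.2, but it may still enter the SAE table, so SAE counts could differ between tables without explanation. With safety as the sole objective, one would want the window for the most serious events to be coherent. The fixed name of the call adds a second doubt: for a subject who stops early, Day 374 may lie many months after the last dose.

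**Working it through.** **Reproducing the call day.** Visit 6 is on Day 360 (Section 4.2.6) and the call follows about 14 days later: 360 + 14 = 374, as stated.

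**Last dose.** Dosing starts on Day 1 (Section 4.2.1). Visits 1 to 5 dispense 2 + 2 + 2 + 3 + 3 = 12 bottles of 30 days each, so 12 × 30 = 360 doses. The protocol does not name the last dosing day. I take Day 360, or Day 359 if no dose is taken on the day of Visit 6.

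**Gap for a nominal completer** = (last dose day + 30) − call day.

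| Last dose | SAE collection ends | Days after the Day 374 call | Share of the 30 days |
|---|---|---|---|
| Day 359 | Day 389 | 15 | 15/30 = 50% |
| Day 360 | Day 390 | 16 | 16/30 = 53% |

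**With the ±4-day windows.** Visit 6 may fall on Days 356 to 364 and the call on Days 370 to 378.

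- Shortest: last dose Day 355, call Day 378, giving 355 + 30 − 378 = 7 days.
- Longest with the last dose no later than Day 360: call Day 370, giving 360 + 30 − 370 = 20 days.
- A gap of 364 + 30 − 370 = 24 days needs a dose on Day 364. That requires leftover drug, since the 360 doses supplied run out on Day 360 if taken daily as directed.

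**Early terminators.** If the call comes 14 days after the early-termination visit and drug stopped *k* days before that visit, the gap is 30 − 14 − *k*. This gives 16 days for *k* = 0, 9 for *k* = 7, and 0 for *k* = 16. If Day 374 is instead read as a calendar day for everyone, the order reverses for any last dose before Day 344 (344 + 30 = 374). A last dose on Day 180, for example, ends SAE collection on Day 210, which is 164 days before Day 374.

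**How much follow-up is involved.**

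- Share of a completer's SAE-collection period: 15/389 = 3.9% to 16/390 = 4.1%.
- All 300 subjects (Section 9.1): 300 × 15/365.25 = 12.3 to 300 × 16/365.25 = 13.1 patient-years. This is slightly high, because some early terminators have a shorter gap.
- SAEs expected at an assumed 2 to 10 per 100 patient-years: 12.3 × 0.02 = 0.25 to 13.1 × 0.10 = 1.3.

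**Do the passages contradict each other?** Section 5.1 governs adverse events in general and Section 6 governs SAEs. The treatment-emergent window in Section 9.3.2 ends where general collection ends in Section 5.1, so those two agree. Only the SAE rule runs longer, which is permissible.

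**Is the mismatch between tables new?** No. SAE collection starts at consent, while the treatment-emergent window starts at first dose. An SAE table not limited to treatment-emergent events can therefore differ from the treatment-emergent tables whatever happens after the call. The table sentence is also ambiguous: if the withdrawal clause qualifies SAEs as well as AEs, a completer's late SAE would not be in that table at all.

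**The case for a change.** The strongest case for a change is that the protocol makes a commitment in Section 6 without scheduling anything to meet it. Section 5.1 tells subjects to report promptly, but the same paragraph ends collection at the call, and nothing says subjects are told to keep reporting afterwards. Following SAEs to resolution covers known events and does not find new ones. For a completer the gap is never zero, even at the extremes of the visit windows. If the withdrawal clause is read as limiting the whole table, a late SAE would be less visible still.

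Most of this stands as description: ascertainment after the call is passive, and the text does not say where a late SAE is counted. It does not carry as far as a change.

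- Stating in which table a late SAE appears only writes down what a competent analyst would do anyway: list the event, mark it as after treatment, and explain any difference in counts.
- Moving the call to about Day 390 has its own price. It gives up the query two weeks after treatment on new and ongoing events and lengthens recall for non-serious ones. It extends participation to 390/7 = 55.7 weeks against the stated 54 or so, and it needs an amendment under Sections 8.1 and 12.3.
- Stretching the treatment-emergent window to 30 days is debatable. The Introduction describes lactitol as little absorbed, if at all, in the small intestine, although its colonic metabolites can be absorbed. Whether an event 15 to 30 days after stopping belongs with on-treatment events is a judgement, and nothing in the protocol requires it.

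The calendar-day reading for early terminators is not the natural one, because Sections 3.3 and 4.2.7 tie the call to the end of treatment or to the early-termination visit. An analyst would use the date of each subject's own call.

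**Conclusion.** The dates are as described: for a nominal completer, SAE collection outlasts the last scheduled contact and the treatment-emergent window by 15 to 16 days (7 to 20 days across the visit windows, with the last dose no later than Day 360). For early terminators the gap depends on when drug stopped relative to the visit and can be zero. No change to the plan follows. The longer SAE period is permissible, a reporting route exists, and the unscheduled days are about 4% of a completer's SAE-collection period. The expected number of SAEs in them is about 0.25 to 1.3. That figure rests on an assumed rate of 2 to 10 per 100 patient-years and on all 300 subjects contributing 15 to 16 days. The safety conclusion does not turn on events of that number. What remains is a gap in wording that analysts fill sensibly, by using each subject's actual call date and showing any later SAE separately. Closing it by moving the call or widening the window would exchange one limitation for another.

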3. STUDY PLAN

3.1. Study Design

This is an open-label, multi-center study in which constipated subjects will receive BLI400 for 12 months.

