9. DATA ANALYSIS

9.1. Sample Size

Consistent with *ICH E1A Guideline for Industry, the Extent of Population Exposure to Assess Clinical Safety: for Drugs Intended for Long-term Treatment of Non-Life-Threatening Conditions (March 1995)*, 300 subjects will be treated with BLI400 for 12 months. This will allow for detection of adverse events that may increase in frequency or severity over time.

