9.4.1. Modified Intention-to-Treat (mITT) Population

This population consists of all enrolled subjects that took at least one dose of study medication. This population will be utilized for all safety analyses.

9.4.2. **Per-Protocol Population**

The per-protocol (PP) population will consist of all subjects in the mITT population who have not violated study entry criteria and have not deviated significantly from the protocol during the course of the study. Any analyses from this population will be considered as supportive to the ITT and mITT analyses. Reasons for exclusion from the PP population will be defined in the clinical study report.

10. **DRUG INVENTORY AND DISPOSITION**

At the conclusion of the study, all drug materials will be accounted for. Federal law requires that, at the conclusion of the study, all drug materials must be returned to the study sponsor or destroyed according to local regulations.

11. **STUDY MONITORING**

A Braintree Laboratories Study Monitor or qualified designee will visit the study center prior to the commencement of the study and periodically during the course of the study in accordance with federal guidelines governing the sponsorship of studies.

12. **DOCUMENTS AND NOTIFICATIONS**

12.1. **Informed Consent**

Written informed consent will be obtained from the subjects by the Investigator and will be kept on file at the study center. Documentation of the consent process should be noted in the study source documents.

12.2. **Institutional Review Board**

Peer review and approval of the protocol by an appropriate Institutional Review Board is required prior to commencement of enrollment. Amendments to the approved protocol must also be submitted to the Institutional Review Board and approved prior to their implementation.

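### Adverse event rates in different periods of a single cohort are to be compared with tests and intervals that assume independent groups

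*Combined protocol and SAP*

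**What the plan says.** The design has one arm. Section 3.1: "This is an open-label, multi-center study in which constipated subjects will receive BLI400 for 12 months". Section 3.3 names one treatment phase: "Qualifying subjects will receive BLI400 at Visit 1 and will begin a 12-month Treatment Period". Clinic visits fall at the end of Months 2, 4, 6, 9 and 12.

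The AE part of Section 9.3.2 sets the comparison: "The difference in adverse event rates between study periods will be tested by Chi-Square or Fisher's exact test with 95% confidence intervals". The same section fixes the unit: "Counting will be done by subject and not by event". Section 9.4.1 defines the mITT set as everyone who took at least one dose, and adds: "This population will be utilized for all safety analyses". The combined document contains the protocol text twice, and the wording is the same in both copies.

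The plan does not define the study periods, give a denominator for each, or name a paired, clustered or repeated-measures method for AEs. Section 9.1 gives the purpose that such a comparison would serve: "This will allow for detection of adverse events that may increase in frequency or severity over time".

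**The concern.** Chi-Square and Fisher's exact test compare two sets of different people. Here the second set is the first set less those who have left. However the 12 months are divided, the two proportions come from overlapping subjects, so their covariance is not zero. Both named tests, and an unpaired interval for the difference, leave that covariance out.

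At stake is the only planned AE test of change over time. Someone prone to an AE in one period is likely to be prone to it in the next. For such terms the planned test has less chance of showing a rise than a paired test on the same data. In a safety study that is the unfavourable direction. The error can also run the other way for terms with a single possible onset, so a reader of the final tables could not apply one mental correction.

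**Working it through.** **Inputs.** From the documents: n = 300 (Section 9.1), 95% intervals and by-subject counting (Section 9.3.2). Assumed, because the documents give no value: two-sided 5% level, two equal periods, all subjects followed through both, the risk per period, and the within-subject correlation phi. The plan has no power figure to reproduce, since 300 is taken from the ICH E1A guideline. As a check on the set-up, with phi = 0 the simulated Chi-Square size was 4.9% to 5.1%. Power for 20% against 30% was 81.0%, against 80.9% by the usual two-proportion formula.

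**Step 1: variance.** For the difference between two period proportions in the same n subjects:

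Var = [p1(1−p1) + p2(1−p2) − 2·phi·√(p1(1−p1)·p2(1−p2))] / n

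The unpaired methods drop the last term. With equal risks the true variance is (1 − phi) times the assumed one. So the interval is 1/√(1−phi) times too wide, and the true error rate is 2[1 − Φ(1.96/√(1−phi))].

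| phi | CI width factor | Error rate by formula | Simulated, 10% risk |
|---|---|---|---|
| 0.1 | 1.05 | 3.9% | 4.0% |
| 0.3 | 1.20 | 1.9% | 2.0–2.1% |

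The nominal 95% interval therefore covers about 96% to 98%. Fisher's test is more cautious still, at 2.9% and 1.4% in simulation.

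**Step 2: power for 10% against 15%.** Power ≈ Φ[(0.05 − 1.96·SE0)/SE], where SE0 is the standard error that the test uses under no difference and SE is the true one. Here √(0.09 × 0.1275) = 0.1071.

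- Chi-Square SE0 = √(2 × 0.125 × 0.875/300) = 0.0270.
- McNemar SE0 = √(discordant proportion/300). The discordant proportion is 0.1986 at phi 0.1 and 0.1557 at phi 0.3, giving 0.0257 and 0.0228.
- True SE = √((0.2175 − 0.0214)/300) = 0.0256 at phi 0.1, and √((0.2175 − 0.0643)/300) = 0.0226 at phi 0.3.

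| phi | Chi-Square, formula | Chi-Square, simulated | McNemar, formula | McNemar, simulated |
|---|---|---|---|---|
| 0.1 | 45.4% | 46% | 49.3% | 50% |
| 0.3 | 44.9% | 45% | 59.3% | 60% |

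Fisher's test has simulated power of 41% and 39%.

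**Step 3: what phi is plausible?** As a scale only, suppose that subjects differ in AE rate by a gamma frailty with coefficient of variation CV, and let theta = CV². P(no AE in one period) = (1 + theta·L)^(−1/theta), and P(no AE in both) = (1 + 2·theta·L)^(−1/theta). At 10% risk and CV 1, L = 0.1111 and P(no AE in both) = 1/1.2222 = 0.8182, so phi = (0.8182 − 0.81)/0.09 = 0.09. CV 2 gives 0.29. The range for CV 1 to 2 is 0.03 to 0.11 at 3% risk, 0.09 to 0.29 at 10%, and 0.23 to 0.56 at 30%.

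**Step 4: uncommon terms.** For 3% against 6% with phi of about 0.03 to 0.1, simulated power is 42% to 43% for Chi-Square and 44% to 48% for McNemar, a loss of about 2 to 5 points.

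**Step 5: terms that can start only once.** No subject can then be positive in both periods, so phi = −p/(1−p). At 5/10/15% risk per period this is −0.05/−0.11/−0.18. The Step 1 formula gives Chi-Square error rates of 5.6/6.3/7.1% on fixed denominators, and simulations gave 5.6% to 7.3%. McNemar's test stays at about 5%. If the second period counts only subjects still free of the event, Chi-Square returns to 5.0% to 5.2%.

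**The case against.** The strongest reply is that this is first a gap in specification. With periods and denominators undefined, nobody can say which way the test errs, and for once-only terms the right denominator removes the inflation. That stands for those terms. It does not rescue terms that can recur, where the same subjects contribute to both periods under any division.

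Second, the practical effect may be small. Section 9.2 plans a descriptive presentation of AE rates, Section 9.1 rests detection on exposure and not on a p-value, and many preferred terms will be uncommon. This also stands, and it limits how much weight the point can carry.

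Three stronger readings are tempting, and the documents do not support them:

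- **A severe loss of power.** At phi 0.5 the gap for 10% against 15% would be 44% against 75%. The documents give no phi, and at 10% risk 0.5 lies above the 0.09 to 0.29 in Step 3.
- **False differences from unequal periods or dropout.** The visit intervals are unequal (2, 2, 2, 3 and 3 months), and a fixed mITT denominator would count people who had left. The plan does not say that periods will follow visits or that denominators will stay fixed.
- **Failure of the study's safety purpose.** The AE, SAE and withdrawal tables do not depend on this test.

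**Conclusion.** The point holds and should be fixed. The subject overlap follows from the design and is certain, and the named methods ignore it. The size is moderate at most. For AEs at about 10% per period with phi of 0.1 to 0.3, the loss is about 4 to 15 points of power and the interval is 5% to 20% too wide; for uncommon terms the loss is slight. For once-only terms on fixed denominators, the error rate rises modestly above 5%. These sizes rest on the assumed risks and correlations, equal periods and complete follow-up, and the documents supply none of these. The effect is confined to this one comparison.

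**What to change.** Replace the sentence in Section 9.3.2, in both copies, with a within-subject comparison:

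1. State periods of equal length in days, for example Days 1–180 and 181–360, and tabulate later AEs separately.
2. Count each subject once per term per period, by onset date. The plan already says "Adverse Events having missing onset dates will be considered as treatment emergent", but it assigns such events to no period. The report date can do that, since under Section 5.1 "The Investigator will record date/time of report, date/time of onset, description of the adverse event".
3. Compare each later period with the first by McNemar's test with a paired 95% CI, in subjects followed through both periods. For several periods or incomplete follow-up, a subject-clustered (GEE) binary model on subjects at risk at the start of the period may be used instead.
4. Tabulate AE proportions on at-risk denominators, and AEs leading to withdrawal, by period. State whether a subject who has stopped drug but awaits the follow-up call counts as at risk.
5. Label the p-values exploratory.

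The cost is a small amendment with the agreement and IRB approval that Sections 8.1 and 12.3 require, plus some programming; no new data are needed. The paired test drops subjects who leave early. Neither method removes bias from withdrawal caused by AEs, which Sections 1 and 8.2 anticipate, so the withdrawal table must be read beside the comparison.

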4. STUDY PROCEDURES

Study procedures are described as follows and depicted graphically in [Section 4.3](#), below. Acceptable deviations from the visit schedule are indicated. These variations must not be cumulative; i.e. visits should always be scheduled in relationship to Visit 1 (Day 0).

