4.2.2. Visit 2 (*Month 2*) +/- 4 days

Subjects will continue to take BLI400 daily and will return to the clinic for Visit 2 (Day 60). Vital signs (see [section 4.1](#) for details) and ECGs will be recorded. Study personnel will weigh returned bottles and count rescue bisacodyl for accountability purposes. Subjects will be queried for any adverse events or changes to their concomitant medications. Subjects will complete the PAC-QOL and PAC-SYM questionnaires. Samples for chemistry, hematology and urinalysis will be repeated as outlined in [Section 4.1](#). Subjects will be dispensed 2 new bottles of study medication. Subjects will be instructed to return all bottles and bisacodyl at the next follow up visit.

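### Section 9.3.2 tests by-subject adverse event proportions between undefined study periods, with no allowance for period length or time at risk, so the test cannot reliably show whether adverse events increase over time.

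*Combined protocol and SAP*

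**What the plan says.** Section 9.3.2 (Adverse Events) commits to a formal comparison over time: "The difference in adverse event rates between study periods will be tested by Chi-Square or Fisher's exact test with 95% confidence intervals". The same section fixes the unit, "Counting will be done by subject and not by event", and the summary measure: "Proportions of subjects with adverse events will be presented for the overall study population". The rates to be tested are therefore proportions of subjects with at least one event.

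Section 9.4 says of the mITT population (at least one dose taken): "This population will be utilized for all safety analyses". Whether a period's denominator is every mITT subject or only those still on study is not stated.

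The term *study periods* is not defined. The only named period is the single 12-month Treatment Period in Section 3.3, which also sets the visit schedule: "Subjects will return for clinic visits at the end of Months 2, 4, 6, 9 and 12". Section 9.1 says of treating 300 subjects for 12 months: "This will allow for detection of adverse events that may increase in frequency or severity over time". The protocol text appears twice in the combined document, with the same wording on these points.

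**The concern.** A proportion of subjects with an event depends on how long they were watched as well as on how often events occur. A 90-day window catches more subjects than a 60-day window at an unchanged rate, and a window that many subjects have left catches fewer. The plan controls neither length nor time at risk.

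Safety is the sole objective of this single-arm study, and the period comparison is the only planned AE test that addresses change over time. If it mixes period length and dropout with the event rate, it could report a late increase for a drug with a flat AE profile, or conceal a real one, depending on choices the plan leaves open.

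**Working it through.** **Nothing to reproduce for N.** The figure of 300 rests on an exposure guideline. Section 9.1 gives no rate, effect size or power.

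**Period lengths.** Visits 1 to 6 fall on Days 0, 60, 120, 180, 270 and 360 (Sections 4.1 to 4.2.6). The differences are 60, 60, 60, 90 and 90 days, total 360. The 30-day bottles dispensed (2, 2, 2, 3, 3) give the same lengths. The telephone call on Day 374 adds a 14-day tail.

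**Assumptions.** These are not in the documents: constant AE hazard; p60 (proportion with an AE in 60 days) from 1% to 30%; two-sided 5% level, matching the 95% intervals; independent samples of 300, as the planned tests assume.

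**No dropout.** p90 = 1 − (1 − p60)^1.5. At 10%, 1 − 0.9^1.5 = 14.6%. The table compares the first interval (60 days) with the last (90 days). Fisher rejection is by exact enumeration of two binomials. The Chi-Square columns are approximations, and the last compares all five intervals (noncentral chi-square, 4 df).

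| p60 | p90 | Ratio | Fisher rejects | Chi-Square rejects | Five intervals |
|---|---|---|---|---|---|
| 1% | 1.5% | 1.50 | 3% | 8% | 9% |
| 2% | 3.0% | 1.49 | 7% | 12% | 14% |
| 5% | 7.4% | 1.48 | 18% | 23% | 30% |
| 10% | 14.6% | 1.46 | 36% | 41% | 56% |
| 20% | 28.5% | 1.42 | 64% | 68% | 88% |
| 30% | 41.4% | 1.38 | 81% | 83% | 97% |

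At 5% and above, almost all of the first-versus-last rejections point to an increase. The pattern is a step at Day 180, not a steady rise. The same arithmetic hides a decline: a daily hazard cut to two thirds over 90 days gives (2/3) × 90 = 60 days' worth of the original hazard, so the proportions match.

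The only AE incidence on lactitol in the documents is 31.2% (Section 1), with no duration. If it covered 360 days (an assumption), p60 = 1 − 0.688^(1/6) = 6.0% and p90 = 8.9%, with about 27% false signals by Chi-Square.

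**With dropout.** The documents give no dropout rate, so a range is shown. Let d be the proportion lost over 360 days, μ = −ln(1 − d)/360, and λ = −ln(0.9)/60 = 0.001756 per day (p60 = 10%). For an interval starting on day a with length L, the share of all mITT subjects with an event is

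e^(−μa) × λ/(λ + μ) × [1 − e^(−(λ + μ)L)].

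For d = 20%, μ = 0.000620. The last interval gives 0.846 × 0.739 × 0.1925 = 12.0%. Dividing by the first factor gives the share of subjects entering the interval, 14.2%.

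| Dropout | Fixed mITT: first vs last | Fisher rejects (fixed mITT) | Entering subjects: first vs last |
|---|---|---|---|
| 0% | 10.0% vs 14.6% | 36% | 10.0% vs 14.6% |
| 20% | 9.8% vs 12.0% | 11% | 9.8% vs 14.2% |
| 40% | 9.6% vs 9.4% | 4% | 9.6% vs 13.7% |
| 50% | 9.5% vs 8.0% | 7% | 9.5% vs 13.5% |
| 80% | 8.8% vs 3.6% | 70% | 8.8% vs 12.1% |

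The true rate is constant in every row. At 50% and 80% dropout, the fixed-denominator rejections are nearly all false decreases.

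**Equal halves alone are not enough.** Day 1-180 against Day 181-360 gives 27.1% in each half with no dropout. On a fixed mITT denominator it gives 25.7% vs 23.0% at 20% dropout and 24.1% vs 18.6% at 40%. At 40%, Fisher's test declares a false decrease about 33% of the time.

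**Person-time.** A constant λ is 0.001756 × 365.25 × 100 = 64.1 per 100 person-years in any interval. An exposure-adjusted comparison of event counts rejected in 4.7% to 4.8% of 20,000 simulated trials, with no dropout and independent counts.

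**Treatment against follow-up.** At the same λ, crude proportions would be 1 − 0.9^6 = 46.9% over 360 days and 1 − 0.9^(14/60) = 2.4% over 14 days.

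**The case against.** The best reply is that the plan never says the periods are visit intervals. Where it means visits it says so, as for laboratory, vital-sign, ECG and questionnaire data. Equal halves bounded by existing visits would comply with the text and carry no length artefact. A reader might infer that the planned analysis will show a false late increase; the documents do not support that. The periods are undefined, and on a fixed mITT denominator, a natural reading of Section 9.4, the direction depends on dropout.

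A reader might also infer that the trial was powered to detect rising AE rates. It was not: 300 is an exposure count, and detection is named as something that exposure allows. Section 9.2 describes the AE rates as descriptive, and no decision rule hangs on the test. Nor does the plan say that treatment will be tested against follow-up; both lie inside one treatment-emergent window. Finally, for individual preferred terms at 1% to 2% per 60 days, false significance is uncommon.

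All of this stands and limits the point. It does not remove it. Crude proportions mislead under both splits the schedule suggests, visit intervals and treatment versus follow-up. Equal halves also fail on a fixed denominator once subjects leave. Nothing in Section 9.3.2 prevents any of these choices, including after the data are seen.

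**Conclusion.** The point holds in a conditional form. The firm defect is a committed test of crude by-subject proportions between periods whose limits and denominators are undefined, with no adjustment for time at risk.

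If the periods are the visit intervals and the denominator is subjects at risk, the apparent increase after Month 6 is 38% to 50% over the rates examined. At 10% per 60 days with no dropout, it is a false Fisher signal in about 36% of trials. On a fixed mITT denominator the artefact is smaller, about nil near 40% dropout, and an apparent decrease above that. These sizes rest on constant hazards for AEs and dropout and on independent samples. In fact the same subjects appear in every period, which the planned tests also ignore.

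The plan should be changed, because this is the only AE test directed at the change over time that Section 9.1 mentions.

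**What to change.** In Section 9.3.2:

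- Define the periods before analysis as Day 1-180 and Day 181-360, by calendar day rather than actual visit date.
- Compare AE onsets per person-time at risk. One suitable method is a Poisson or negative binomial model with log person-time as offset and subject-clustered standard errors, reporting the rate ratio with its 95% interval. Alternatively, compare proportions among subjects on study at the start of each period, accounting for follow-up time and for the same subjects appearing in both.
- If visit intervals are shown, give AE onsets per 30 person-days at risk.
- Do not test treatment against the 14-day follow-up on crude proportions.
- State how events with missing onset dates are placed. The present rule makes them treatment-emergent but assigns no period.

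By-subject counting can stay for the incidence tables. The cost is a few sentences, slightly more analysis work and coarser time resolution. Section 5.1 already requires onset date and time, so no new data are needed. Person-time does not correct for subjects leaving because they tolerate the drug poorly, so AE withdrawals should be shown by period beside the rates.
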